11.3 Participant Enrollment and Follow-Up

We anticipate enrolling a total of 14,400 participants:

- 1600 index cases in the routine contact investigation arm in Limpopo

- 1600 index cases in the routine contact investigation arm in Soshanguve

- 800 index cases in the holiday contact investigation arm in Limpopo

- 800 index cases in the off-peak contact investigation arm in Soshanguve

- 9,600 contacts (a mean of two contacts per case, accounting for some cases who will not have any contacts, based on our enrollment of contacts in our current trial in Limpopo)

Among adults from the above groups, 384 individuals (192 index cases and 192 contacts) will be selected to participate in the bioethics supplement.

We plan a single visit to each participant, so follow-up is not considered in this study.

11.4 Analysis Plan

Primary Outcome:

Our primary effectiveness outcome will be the ratio of the number of secondary TB cases identified and started on treatment per index case in the novel strategy arm (off-peak screening in Soshanguve and holiday screening in Limpopo) compared to index cases receiving standard contact investigation. We will conduct separate analyses for each site (rural Limpopo and peri-urban Soshanguve). For the primary analysis we will conduct an unpaired t-test for the hypothesis that the difference between the number of secondary TB cases per index case is the same in the two study arms. A secondary analysis will be performed to adjust for index case demographics, socio-economic factors, self-reported health seeking behavior, and clinical characteristics such as HIV status and history of TB. As the majority of the index cases are expected to have no secondary cases, this will be conducted using a zero-inflated Poisson regression with robust standard errors to account for household and enrollment site clustering.

Secondary outcome measures:

1. The TB prevalence ratio, comparing highly mobile to less mobile index patients, measuring mobility on two scales (neighborhood/intra-urban and regional/intra-national). For the former, we will estimate the number of kilometers traveled on a daily basis (secondary analysis: amount of time spent in transit), truncating long excursions at 50km (one hour). Based on exploratory data analysis and consideration of generalizable numbers (e.g., multiples of 5 and 10), we will consider a binary measurement of "highly mobile" versus "less highly mobile" at a natural break near the midpoint of the data. We will then use logbinomial regression to adjust for a priori potential confounders that will include age, sex, socioeconomic status, and HIV status, and robust variance estimation to account for clustering by households. Analyses will be stratified by site. We will perform a similar analysis for regional/intra-national mobility, taking as the primary exposure variable the self-reported number of trips per year greater than 50km (secondary analysis: number of nights spent away from primary residence). For each measure of mobility, we will explore additional methods of modeling the exposure variable, including continuous (linear), using restricted cubic splines (which may yield less interpretable estimates of effect but more flexible incorporation of complex patterns in the data), and as a categorical ("dummy variable") exposure – again at natural breaks in the data.

- 2. TB strain relatedness using maximum likelihood transmission trees. Along with standard genetic thresholds (i.e. SNP differences of <5) for assessing whether strains are related by transmission, we will construct a maximum-likelihood phylogenetic tree using RAxML and other tree estimation packages. We will then employ a Bayesian approach to infer transmission.^{65,66} After separating the data into distinct putative transmission clusters using a probabilistic approach combining SNPs, timing, and location information, we will generate timed phylogenetic trees for each cluster using Bayesian Evolutionary Analysis Sampling Trees (BEAST).¹¹⁶ We will then use a stochastic, continuous-time Monte Carlo Markov Chain (MCMC) representing a branching transmission model. We will model within-host evolution of Mtb assuming a neutral coalescent process and generate transmission trees using an MCMC approach.^{65,67} We will weight candidate transmission trees based on likely or unlikely linkages (e.g., household contacts). This method integrates TB natural history, epidemiological, and WGS-derived phylogenetic data into a statistical modeling framework to draw probabilistic conclusions about the likelihood of transmission between persons. "Transmitters" will be defined as individuals from whom at least one secondary case most likely originated.
- 3. Relative acceptability of each novel strategy. We will create an acceptability score from the interview questions, with a higher score indicating greater acceptability of the contact tracing strategy. We will use multivariable generalized linear regression model with a suitable link to model the acceptability score, with the primary exposure of interest being each novel contact investigation strategy (i.e off-hours tracing in Soshanguve, holiday tracing in Limpopo), relative to standard contact investigation in each setting. Analyses will be stratified by site
- 4. Feasibility of each strategy as the proportion of potentially eligible index cases for whom a household visit was conducted. We will also record all reasons why visits were unable to be conducted (e.g. could not find household, no one ever home, visit not conducted during expected off-peak period). Analyses will be stratified by site
- 5. Relative fidelity of each novel strategy using a process checklist for each index case and household, including whether the household visit was offered and accepted, whether the visit was attempted, whether the visit was successful (i.e., enrolled at least one contact), whether symptom screening and sputum collection were completed and whether newly identified TB cases were notified and referred for treatment. We will model fidelity as a binary outcome, using log-binomial regression, with the primary exposure of interest being novel versus standard contact investigation (separately in each setting), adjusting for potential confounders (for example, socio-demographic and clinical factors) and enrollment site as with the acceptability outcome and robust standard errors for multiple outcomes per household. Analyses will be stratified by site

- 6. Sustainability of each novel strategy will be accomplished by incorporating an indicator variable for the six-month time windows of the study period into the multivariable regression models of acceptability and fidelity outcomes described above, and evaluating for interactions between this time window indicator and the primary exposure variable (i.e. investigation arm).
- 7. Cost-effectiveness ratio for each novel strategy. Outcome measures will be derived by combining study data on patient characteristics (e.g., demographics, HIV status) and intervention effectiveness with literature estimates on key parameter values (e.g., disability weights,68 sensitivity of Xpert Ultra,69 and notified data on treatment outcomes¹) to construct a Markov model of a population of individuals who are eligible for TB screening under each strategy. In performing this evaluation, we will follow standard guidance for economic evaluation, including inflation using South Africa's GDP deflator, conversion to a common currency (US dollars) and year, discounting of all future costs and effectiveness, and measurement of costs as economic (opportunity) costs.^{70,71} We will conduct one-way sensitivity analyses of all model parameters and multiway sensitivity analyses of those parameters found to be most influential, in order to provide insight into the major drivers of cost-effectiveness and the settings in which each contact tracing strategy is likely to be preferred. We will also perform a probabilistic sensitivity analysis (using beta distributions for parameters with defined upper and lower bounds and gamma distributions for parameters defined from zero to infinity) to generate 95% uncertainty ranges around all estimates. We will construct cost-effectiveness acceptability curves, using as a reference South Africa's per-capita gross national income of \$5,430 as a willingness to pay per DALY averted⁷² but also considering revealed thresholds for potentially competing interventions (e.g., the estimated cost-effectiveness of treatments for MDR-TB for which the government of South Africa has revealed a willingness to pay).
- 8. Experiences of inconvenience, attitudes toward confidentiality, motivation to participate, and preferences for disclosure. Outcome measures will be assessed via Likert scales which will be evaluated via multivariable regression, adjusting for demographic characteristics, district, study arm, and household characteristics (e.g., size). Responses will be dichotomized based on exploratory data analysis and conduct log-binomial regression, comparing these results to those of linear regression performed after assigning a numerical value to each response level. Our generic (e.g. unlabeled) discrete choice experiment (DCE) will be based on five different attributes (disclosure of index case TB status, routine vs off-peak evaluation, inclusion of routine HIV testing, use of official vs unmarked cars, provision of monetary reimbursement for time), each with two different levels. The DCE will utilize a fractional factorial design created to estimate the main effects alone. Results from the DCE for certain characteristics

will be compared against a double-bounded contingent valuation survey in which we will evaluate participants' willingness to accept household CI (with different characteristics) with and without monetary reimbursement of different levels (to compensate for household members' time).

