11.2 Sample Size Considerations

We estimate our sample size based on the assumption that 3% of household contacts will have tuberculosis (half the 6% prevalence seen in a previous study led by [name]),⁶⁴ and that an average of two contacts per case will be screened in the routine arm (based on our ongoing trial in Limpopo). Thus, in the routine arm, we anticipate a mean of 0.06 secondary cases per index case. Given the additional complexity of holiday-time or off-peak screening, we power our analysis under the *a priori* belief that such interventions will not be reasonably implemented unless they result in a yield that is twice that under routine contact investigation. Assuming an average of two to five contacts per household and a high (0.68) between-household coefficient of variation of the outcome as found in ⁶⁴, a comparison of n=1600 households (index cases) in the routine arm and 800 households (index cases) in the novel arm would have more than 99% power to detect this difference. If only half of the expected index cases are enrolled, the minimum power (two contacts per household) would be 84%. A maximally conservative estimate of sample size – assuming complete clustering of these cases at the household level, two contacts per household, and only 50% as many household cases.

We have selected our sample size to give more than 90% power to detect this most conservative difference. The table below provides estimates of our power to detect a statistically significant difference in the primary outcome.

Table. Power calculations. The power to detect each difference is given in italics; the primary comparison is between finding 0.06 secondary cases per index case in the routine arm and 0.12 in the novel screening arm.

		Mean number of secondary cases per index case, novel approach										
		0.08	0.1	0.12	0.18	0.24						
un er of dary per per case case ine	0.02	>0.99	>0.99	>0.99	>0.99	>0.99						
	0.04	0.99	>0.99	>0.99	>0.99	>0.99						
Me numk secor secor case: index , rou , rou	0.06	0.54	0.97	>0.99 (primary)	>0.99	>0.99						
	0.08	-	0.44	0.93	>0.99	>0.99						

Randomization

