Randomization will be performed using computer-generated random permuted blocks of varying sizes, with an allocation ratio of 2 (routine):1 (novel: holiday or off-peak). Randomization will be conducted separately for Limpopo and Soshanguve and surrounding areas (i.e., two separate randomization sequences will be generated for each site); and within Limpopo, randomization will be further stratified by district, thus ensuring 2:1 allocation within each district as well. The randomization schedules will be uploaded into the REDCap system, which will automatically output an allocation every time a new consented patient is added and the interview is completed. In Limpopo, randomization will be performed throughout the year; those patients who are allocated to holiday timing will undergo household contact investigation during Easter if they are enrolled between February 1 and the end of the two-week Easter holiday, whereas those patients enrolled between the end of the Easter holiday and December 31 will undergo contact investigation during Christmas.

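### The primary t-test does not state its variance form; if variances are pooled, its standard error is about 11% too small at the planned effect

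*Combined protocol and SAP*

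**What the plan says.** The primary test is given in section 11.4: "For the primary analysis we will conduct an unpaired t-test". Its null hypothesis is that mean yield does not differ between the arms. It is applied by setting: "We will conduct separate analyses for each site (rural Limpopo and peri-urban Soshanguve"). The text does not say whether the variances are pooled, and it gives no significance level, sidedness or confidence interval for this comparison. Robust standard errors are specified in 11.4 for the secondary adjusted zero-inflated Poisson model, but not for the primary test.

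The design figures are in section 11.2. Randomization is "with an allocation ratio of 2 (routine):1 (novel: holiday or off-peak"), so each setting has "a comparison of n=1600 households (index cases) in the routine arm and 800 households (index cases) in the novel arm". On the effect, "the primary comparison is between finding 0.06 secondary cases per index case in the routine arm and 0.12 in the novel screening arm". The sample size also assumes a "high (0.68) between-household coefficient of variation of the outcome". The same section says that the novel strategies would not reasonably be adopted unless they at least double the routine yield.

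**The concern.** A pooled t-test assumes equal variances. A rare count does not have them when the means differ: at 0.06 against 0.12 the novel arm has about twice the variance of the routine arm. It also has half the index cases. The pooled variance is then weighted towards the larger, less variable arm, while the true uncertainty comes mainly from the smaller, more variable one. In that configuration pooling understates the standard error.

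Because 11.4 leaves the form open, two analysts could both follow it and report different p-values and different intervals. Precision matters here because section 11.2 ties adoption to the size of the yield and not only to its being above zero. An interval that is too narrow around a real benefit makes the evidence on size look firmer than it is.

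**Working it through.** **Inputs.** From 11.2: means 0.06 (routine) and 0.12 (novel); 1,600 and 800 index cases per setting; between-household coefficient of variation (CV) 0.68. The documents give no standard deviation. I assume a Poisson count whose household rate varies with CV 0.68, so that variance = m + (0.68m)². I also assume a two-sided 5% level, because none is stated.

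**Variances.**
- Routine: 0.06 + (0.68 × 0.06)² = 0.0617.
- Novel: 0.12 + (0.68 × 0.12)² = 0.1267.

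**Unpooled (correct) standard error.** √(0.0617/1600 + 0.1267/800) = 0.01403.

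**The plan's own figure.** The planned difference over this standard error is 0.06/0.01403 = 4.28. Power is Φ(4.28 − 1.96) = 0.990, or 0.992 for a plain Poisson count. This agrees, to rounding, with the stated power of more than 99%. With half the enrolment (800 and 400), the same formula gives 0.856 against the stated 84%. The inputs are therefore close to those behind the plan's power statements for this effect.

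**Pooled standard error.**
- Pooled variance: (1599 × 0.0617 + 799 × 0.1267)/2398 = 0.0833.
- Standard error: √(0.0833 × (1/1600 + 1/800)) = 0.01250.
- Ratio to the correct value: 0.01250/0.01403 = 0.891, so about 11% too small.

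**Coverage of a pooled 95% interval.** 2Φ(1.96 × 0.891) − 1 = 91.9%. In 20,000 simulated trials, coverage was 92.0% pooled and 94.9% with Welch. The half-widths are 1.96 × 0.01250 = 0.0245 and 1.96 × 0.01403 = 0.0275.

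**Sensitivity to the assumed variance (0.06 against 0.12).**

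| Variance model | Standard error ratio | Pooled coverage |
|---|---|---|
| Poisson | 0.894 | 92.0% |
| Poisson with CV 0.68 | 0.891 | 91.9% |
| Binary | 0.903 | 92.3% |
| Complete household clustering | 0.899 | 92.2% |

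**Dependence on the effect (routine 0.06, CV 0.68).**

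| Novel mean | Standard error ratio | Pooled coverage |
|---|---|---|
| 0.03 | 1.120 | 97.2% |
| 0.06 | 1.000 | 95.0% |
| 0.08 | 0.952 | 93.8% |
| 0.10 | 0.917 | 92.8% |
| 0.12 | 0.891 | 91.9% |

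**Type I error.** With both arms at 0.06 and the same distribution, the simulated rejection rate was 5.0% pooled and 5.2% with Welch (CV 0.68).

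**Significance at the planned effect.** The expected test statistic is 0.06/0.01250 = 4.80 pooled and 4.28 unpooled. Both are far beyond 1.96.

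**The case against.** The strongest reply is that the plan never says equal variance. Unpaired means only that the samples are independent, and Welch's test is also an unpaired t-test. This stands: the documents show an unspecified form, and the 92% figure is conditional on pooling.

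Second, no interval for the difference is planned. The t-test is stated as a hypothesis test, and the outcome is described as a ratio: "Our primary effectiveness outcome will be the ratio of the number of secondary TB cases identified and started on treatment per index case". This also stands. The coverage figure describes any interval derived from the pooled test, not one the plan promises.

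Third, no conclusion changes at the planned effect, since power is about 99% under either form. That is correct and limits the severity. It does not help a reader who wants to know how large the benefit is.

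A reader might go further and infer that the primary test has an inflated type I error, because equal mean yield could hide unequal variance. The rationale does allow for such a mechanism: holiday visits are deferred (section 4), failed or declined visits count as zero (section 6.1), and more people may be at home when a visit succeeds. The documents do not support a material excess, however. Take an extreme contrast at 3% prevalence, with two contacts in every routine household and four in half of the novel households. Sections 5.1 and 11.3 already contradict its routine side, because their mean of two contacts allows for cases with none. The plan's CV implies a within-household correlation of about 0.68² × 0.03/0.97 = 0.014. At that value:
- Routine variance: 2 × 0.03 × 0.97 × 1.0143 = 0.0590.
- Novel variance: 0.5 × (4 × 0.03 × 0.97 × 1.0429) + 0.5 × 0.12² − 0.06² = 0.0643.
- The standard error ratio is 0.986, so type I error is 2 × [1 − Φ(1.96 × 0.986)] = 5.3%.

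A material excess needs contact patterns that differ strongly between arms at equal means, together with much stronger clustering than the plan's CV implies.

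**Conclusion.** The point holds as a gap in specification with a conditional consequence. If the test in 11.4 is run pooled, the standard error is about 11% too small at 0.06 against 0.12, and a 95% interval from it covers about 92%. That size rests on the planned means and arm sizes and on a variance that rises with the mean. It barely changes across the four variance models tried (coverage 91.9% to 92.3%). It is smaller for smaller benefits, absent at equal means when the arms share one distribution, and conservative if the novel arm does worse. The documents do not support reading this as a failure of type I error control or as a threat to power. Severity is minor to moderate.

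**What to change.** In section 11.4, replace the bare reference to an unpaired t-test with the Welch (unequal-variance) t-test. A linear regression of secondary cases on arm with HC2 or HC3 robust standard errors would serve equally well. State that the difference in secondary cases per index case will be reported in each setting with the matching 95% confidence interval.

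This takes one sentence and no change to the design, sample size or data collection. At the planned effect the interval becomes about 12% wider (0.01403/0.01250 = 1.12), and simulated power remains above 99% (99.6% pooled, 99.4% Welch). Naming the variance form does not settle whether the ratio or the difference is the primary scale. If the ratio stays as the headline measure, its interval method needs its own statement.

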Index cases will represent a sample of consecutive consenting individuals diagnosed with pulmonary TB (including microbiological and/or chest x-ray diagnosis) from twelve hospitals in Vhembe and Capricorn Districts of Limpopo, and 33 primary health care clinics and two district hospitals in Soshanguve and surrounding areas. The only exclusion criteria will be a plan not to pursue treatment within the study district (as this would make contact investigation infeasible in the programmatic setting), and being on TB treatment for longer than one month (as these cases will likely be negative by liquid culture in order to identify transmission links between cases using whole genome sequencing). Note that contacts do not have the same requirement of planning to pursue treatment within the district; thus, it is possible - and expected - that holiday contact investigation in Limpopo will yield cases from outside the district, for example. Individuals who later decline to have contact investigation performed (or who, for example, provide false contact information thus making contact investigation infeasible) will still be included in the study sample and in the denominator for all analyses. Our aim is to make the population of this study as representative as possible as the target population for the proposed intervention. Eligible participants in the bioethics sub-study will include all individuals who were enrolled in the parent study and completed follow-up for the primary outcome (including those who declined or were ineligible to participate in household contact investigation). We will enroll consecutive eligible participants in each district until our desired sample size (64 evaluable index cases and 64 evaluable household contacts from each district) has been attained.

Eligibility Criteria

Subjects in each of the below participant categories must meet each eligibility criteria for that category:

TB index cases:

Inclusion criteria:

- Age 0-99 years (Including those recently deceased)
- Diagnosed with pulmonary TB at a study hospital or clinic (microbiological and/or chest x-ray diagnosis)

Exclusion criteria:

- Unwilling/unable to provide informed consent (including next of kin, for those recently deceased)
- Plan not to pursue TB treatment within the study district
- Unwilling/unable to comply with study procedures

Contacts:

Inclusion criteria:

- Age 0-99 years (18-99 for the bioethics sub-study)

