
Data Collection: Contact tracing and interviews

Upon enrollment, we will conduct a detailed interview of all index cases, based on our current case report forms used in Limpopo. These interviews will include demographic, socio-economic and clinical characteristics, detailed data on mobility and migration, the preceding diagnostic cascade and symptom history, and extensive assessment of costs (including catastrophic health expenditures). Experience suggests that we can collect these data in 30 minutes. For patients

who are deceased or too ill to participate, the next of kin will complete the interview to the best of their ability. We will also collect a sputum sample from each living index case which will be sent for liquid MGIT culture in order to perform whole genome sequencing. After completing the interview, for cases assigned routine or off-peak contact investigation, an appointment time in the next two weeks will be arranged for the household visit. Cases allocated to holiday-time investigation will be asked for contact information and will be called within two weeks of the holiday to remind them of the study and set an appointment time for the household visit.

Study teams (2 in Limpopo and 2 in Soshanguve) consisting of a nurse and a research assistant trained in HIV counselling and testing will visit the household of each consenting index case (or legal guardian, in the case of minors). At the household, teams will recruit all available household members of all ages. For each enrolled participant, the team will conduct a similar interview to the index case on demographic, socio-economic, mobility/migration, health seeking behavior and clinical characteristics. Specifically, mobility questions will focus on spatial and temporal movement patterns over the previous year and will include: number and duration of trips away from primary residence, total duration of time away, destination and purpose of trips, longest distance travelled, longest trip duration, length of time living at primary residence and total number of lifetime moves. Each participant will be screened for TB as described above. Results on Xpert testing will be monitored by study staff using the electronic NICD laboratory system (tier.net), and participants will be notified either by phone or in person at a household visit if they have tested positive for TB and referred to the nearest public-sector clinic for treatment.

Empirical Assessment of Costs

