8.1.2 Secondary Outcome Measures

- 1. The TB prevalence ratio, comparing highly mobile to less mobile individuals, measuring mobility on two scales (neighborhood/intra-urban and regional/intra-national).
- 2. Relative acceptability of each novel strategy, compared against routine contact investigation. We will create a continuous score from the acceptability interview questions (provided to a randomly selected 15% of the population), with a higher score indicating greater acceptability of the contact tracing strategy.
- 3. Feasibility of each strategy as the proportion of potentially eligible index cases for whom a household visit was conducted.
- 4. Relative fidelity of each novel strategy using a process checklist for each index case and household, including whether the household visit was offered and accepted, whether the visit was attempted, whether the visit was successful (i.e., enrolled at least one contact), whether symptom screening and sputum collection were completed and whether newly identified TB cases were notified and referred for treatment.
- Sustainability of each novel strategy by reporting the primary outcome and fidelity measures according to six-month time period over the course of the study.
- 6. Incremental cost-effectiveness ratio for each novel strategy. defined as (cost of contact tracing strategy 2 cost of strategy 1)/(effectiveness of strategy 2 effectiveness of strategy 1), where effectiveness is modeled as the number of disability-adjusted life years (DALYs) averted by the intervention. The primary cost-effectiveness measures will be the incremental cost per DALY averted using novel strategies (holiday and off-hours contact tracing) compared to routine contact tracing in each setting separately.

7. Experiences of inconvenience, attitudes toward confidentiality, motivation to participate, and preferences for disclosure, assessed through both thematic analysis of in-depth interviews and focus group discussions and quantitative analysis of discrete choice experiments and best-worst scaling.

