11 STATISTICAL CONSIDERATIONS

11.1 Study Outcome Measures

Primary Outcome Measure:

Our primary effectiveness outcome will be the ratio of the number of secondary TB cases identified and started on treatment per index case, comparing index cases allocated to the novel strategy (off-peak screening in Soshanguve and holiday screening in Limpopo) to those receiving standard contact investigation.

Secondary Outcome Measures:

- The TB prevalence ratio, comparing highly mobile to less mobile individuals, measuring mobility on two scales (neighborhood/intra-urban and regional/intra-national). For the former, we will estimate the number of kilometers traveled on a daily basis (secondary analysis: amount of time spent in transit), truncating long excursions at 50km (one hour).
- 2. TB strain relatedness using maximum likelihood transmission trees. We will integrate TB natural history, epidemiological, and WGS-derived phylogenetic data into a statistical modeling framework to draw probabilistic conclusions about the likelihood of transmission between persons. "Transmitters" will be defined as individuals from whom at least one secondary case most likely originated.
- Relative acceptability of each novel strategy, compared against routine contact investigation. We will measure acceptability of the intervention among index cases and contacts using a short questionnaire given to a randomly selected participant at a randomly selected 15% of the households visited. The interview will cover acceptability of the visit timing, notification, visit activities (TB screening, HIV testing) and study team interaction among others.
- 4. Feasibility of each strategy as the proportion of potentially eligible index cases for whom a household visit was conducted. We will also record all reasons why visits were unable to be conducted (e.g. could not find household, no one ever home, visit not conducted during expected off-peak period).
- 5. Relative fidelity of each novel strategy using a process checklist for each index case and household, including whether the household visit was offered and accepted, whether the visit was attempted, whether the visit was successful (i.e.,

enrolled at least one contact), whether symptom screening and sputum collection were completed and whether newly identified TB cases were notified and referred for treatment.

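### The TB prevalence ratio by mobility is defined in index patients, who all have TB by eligibility, and no section names a population in which it can be estimated

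*Combined protocol and SAP*

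**What the plan says.** Section 11.4, secondary outcome 1, gives the estimand as "The TB prevalence ratio, comparing highly mobile to less mobile index patients, measuring mobility on two scales". It is the only section that sets out the model. It dichotomises mobility near the middle of the data after exploratory analysis, and then says "We will then use logbinomial regression to adjust for a priori potential confounders" (age, sex, socioeconomic status and HIV status). It adds "robust variance estimation to account for clustering by households" and stratifies by site.

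Section 5.1 makes this an inclusion criterion for index cases: "Diagnosed with pulmonary TB at a study hospital or clinic (microbiological and/or chest x-ray diagnosis".

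Sections 8.1.2 and 11.1 open the same outcome with "The TB prevalence ratio, comparing highly mobile to less mobile" but finish the phrase with *individuals*. Neither says which individuals. For the neighbourhood scale, 11.1 adds "we will estimate the number of kilometers traveled on a daily basis".

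Section 6.1 provides for every enrolled household member to be interviewed in much the same way as the index case, including on mobility, and to be screened for TB. On content it says "mobility questions will focus on spatial and temporal movement patterns over the previous year". The items it then names cover trips, time away, destinations, longest distance and moves.

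**The concern.** A prevalence ratio needs people with and without the disease. Index patients enter the study because they have TB, so the outcome in 11.4 is constant. An analyst who follows the text has nothing to estimate.

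The other sections do not settle what was meant. Household clustering suggests several people per household, and so contacts, but no section says that. Three readings are open:

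- index patients only, as 11.4 says;
- all participants, as *individuals* in 8.1.2 and 11.1 could suggest;
- TB in contacts, grouped by the mobility of their index patient.

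These are different estimands, and the second can produce an association from recruitment alone. The mobility cut-point is already to be chosen after looking at the data. If the population is also left open, a second choice that affects the result is made at analysis.

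**Working it through.** The plan gives no sample size, power or effect size for this outcome, so there is no stated figure to reproduce. The power table in 11.2 concerns the primary outcome only.

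**Inputs from the documents**

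- 4,800 index cases and 9,600 contacts (5.1, 11.3), so 2,400 index cases and about 4,800 contacts per setting.
- TB in contacts: 3% (11.2, "based on the assumption that 3% of household contacts will have tuberculosis").
- Mobility cut near the midpoint (11.4), taken as 50:50.

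**Assumptions, not in the documents:** two-sided alpha 0.05; design effect 1.0 to 1.5; the share of index patients who are highly mobile, varied from 40% to 60%.

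**1. Index patients only.** Ratio = (cases/n, highly mobile) / (cases/n, less mobile). In one setting this is (1,200/1,200) / (1,200/1,200) = 1. Any other split gives the same result, and no mobility effect can be estimated.

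**2. Index patients pooled with contacts.**

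- Contact TB cases: 9,600 × 0.03 = 288.
- Share of all TB cases that are index cases: 4,800 / (4,800 + 288) = 94.3%.
- If the novel arms double the yield, contact cases are 6,400 × 0.03 + 3,200 × 0.06 = 384, and the share is 4,800 / 5,184 = 92.6%.

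Now suppose no association between mobility and TB in contacts, with 7,200 of 14,400 people highly mobile. If 60% of index patients are highly mobile, the highly mobile group holds 2,880 index patients and 4,320 contacts, and the less mobile group holds 1,920 and 5,280:

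- highly mobile: (2,880 + 0.03 × 4,320) / 7,200 = 0.418
- less mobile: (1,920 + 0.03 × 5,280) / 7,200 = 0.289
- ratio: 1.45

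| Index patients highly mobile | Pooled crude ratio, no association in contacts |
|---|---|
| 40% | 0.69 |
| 45% | 0.83 |
| 50% | 1.00 |
| 55% | 1.20 |
| 60% | 1.45 |

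**3. Contacts only.** Per setting there are 4,800 contacts, 2,400 per mobility group, and 4,800 × 0.03 = 144 expected TB cases. With overall prevalence fixed at 3% and true ratio R:

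- p0 = 0.06 / (1 + R) and p1 = R × p0
- SE(log R) = √{DE × [(1 − p0)/(2,400 p0) + (1 − p1)/(2,400 p1)]}
- power = Φ(log R / SE − 1.96)

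| R | p0 vs p1 | SE, DE 1.0 | Power | SE, DE 1.5 | Power |
|---|---|---|---|---|---|
| 1.5 | 2.4% vs 3.6% | 0.168 | 68% | 0.205 | 51% |
| 2.0 | 2.0% vs 4.0% | 0.174 | 98% | 0.214 | 90% |

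Solving for 80% power gives R of about 1.61 (DE 1.0) to 1.80 (DE 1.5).

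The 3% figure matters. Section 11.2 calls it half of the 6% seen in an earlier study. If the novel arms double the yield, there are 384 / 2 = 192 cases per setting, or 4%. Power at R = 1.5 is then 63% to 80%, and the detectable ratio is 1.50 to 1.65. At 6%, power is 81% to 93% and the detectable ratio 1.38 to 1.49.

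**The case against.** The strongest reply is that 11.4 meant TB among contacts, classified by their index patient's mobility. That quantity can be estimated, it keeps the words of 11.4, and it fits the household-clustered variance. On that view the outcome lacks information only when read literally. This is right as far as it goes. But no section states that reading, and its exposure is not the individual's own mobility, which is the natural sense of 8.1.2 and 11.1. The three sections would still have to be reconciled.

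Four lesser points deserve weight:

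- The pooled ratios are crude, ignore the planned adjustment and stratification, and use index mobility shares that have no source in the documents. They illustrate a possible misreading and do not measure an error in the plan.
- The power figures depend on 3% prevalence, and higher contact yield improves them, as shown. A design effect of 1.5 is on the cautious side: with two contacts per household, 1 + (2 − 1) × ρ = 1.5 requires an intra-household correlation of 0.5.
- The mobility items listed in 6.1 are not exhaustive, and no fuller list is given for index cases. The absence of daily distance is a matter to confirm and does not show a gap.
- This is an observational secondary outcome with no power claim, and being listed first implies no hierarchy.

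These points limit the consequences. They do not supply the missing population.

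**Conclusion.** The concern holds. As written in the only section that specifies the analysis, the outcome is constant and the prevalence ratio is 1 whatever the data. No other section names a population that would repair it. This follows from the eligibility criteria and needs no assumption.

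The pooled alternative would be dominated by recruitment: 94% of cases at the plan's own 3%. It could mislead in either direction. A contact-only analysis is feasible, but its precision per setting is limited: a ratio of 2.0 would very probably be detected, while a ratio of 1.5 has 51% to 68% power at 3% prevalence and more if contact yield is higher. Those figures rest on the alpha, split and design effect stated above.

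This should be fixed before analysis. It does not touch the primary outcome or the sequencing objective (1d).

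**What to change.** Use the same definition in 8.1.2, 11.1 and 11.4:

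- **Population:** enrolled household contacts who were screened for TB.
- **Outcome:** TB diagnosed through the household investigation.
- **Exposure:** the contact's own mobility, on each of the two scales.

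Keep the site stratification and household-robust variance already in 11.4. Consider study arm as a covariate, since visit timing affects which contacts are reached. Say that the estimate applies to contacts present at the visit. Use index patients' mobility descriptively or in the sequencing analysis. If the sponsor did intend contacts' TB by index patient mobility, that should be stated as a separate, named estimand.

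Confirm that the contact interview records daily distance travelled and time in transit. If it does not, add the questions, or state that the neighbourhood-scale analysis cannot be done in contacts.

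The cost is a wording change in three sections and possibly an added interview item. The result should be reported with its confidence interval as an estimate of limited precision, based on about 144 contact TB cases per setting at 3%.
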